### Study Interventions

Patients will be randomized to routine stroke care governed by current guidelines (control group) or to emergency endovascular revascularization. Endovascular mechanical revascularization may be undertaken with any currently available and approved device or paradigm and used according to the manufacturers specifications for use.

### Endovascular Intervention

Regulatory agency approved devices may be used (stentriever, aspiration devices). Endovascular intervention may include the administration of intra-arterial thrombolytic (eg. tPA) and the use of balloon angioplasty or guidewire manipulation of thrombus. Endovascular intervention may include direct aspiration of the thrombus through a large bore access catheter. It is not recommended that permanent stents be left in the intracranial circulation or in the internal carotid artery. Guidelines for recommended approaches to endovascular revascularization are reported in Appendix 1.

### Guidelines-based Care – the Control Group

Acute stroke patients should receive the best standard of care according to national guidelines. The model will be the Canadian best practices guidelines for acute stroke care. These are very similar to the guidelines of the American Stroke Association and the European Stroke Organization.

In brief, we expect –

- A. Patients who are appropriate candidates for intravenous thrombolytic therapy within 4.5 hours of defined stroke onset to get rapidly administered IV therapy.
- B. All patients to be managed urgently with attention to physiology. Airway, breathing and circulation first. Fluids – usually normal saline - should be administered as most patients are slightly hypovolemic. Blood pressure should not be aggressively treated other than to guidelines to allow thrombolytic therapy.
- C. All patients should be managed on a stroke unit which should include early mobilization, early rehabilitation, DVT prophylaxis, swallowing assessment and prevention of aspiration pneumonia, NG feeding as appropriate and delayed (up to 4 weeks) placement of PEG tubes in the uncommon instance that these are needed.
- D. All patients should receive ASA therapy (minimally) within the first 48h of stroke but after a day +1 brain image shows no evidence of hemorrhage.
- E. Patients should not receive intravenous unfractionated heparin.
- F. All patients should be thoroughly investigated to sort out the mechanism of stroke and appropriate stroke prevention strategies implemented. There is little use in working very hard on a technical and aggressive approach to acute stroke if it is to be undone on day +10 with a recurrent embolus because a patient has not been effectively treated for a preventable cause of stroke.
- G. All patients should have relevant and appropriate stroke rehabilitation therapy.

In summary, we expect that all patients should have excellent, guideline based stroke care through the full 90 days. These are outlined in our Guidance Document for Best Medical Care.

### Speed of Intervention

A key principle of the endovascular intervention is that it must be both fast and safe. The target non-contrast CT to revascularization time is 90 minutes or less. This will be measured from the time of the first slice of the baseline non-contrast CT head done at the ESCAPE centre. The target complication rate is less than 1%. The quality of intervention will be ensured by hand-selection of sites and only be approved by the executive committee after a site visit. All sites must submit evidence within the 2 years prior to commencement of the trial that they can meet the 90-minute target of CT-to-recanalization time.

A key and critical component of the trial will be an ongoing quality assurance program to ensure that sites can meet these targets for endovascular intervention. Training will be undertaken at the sites and continued on a quarterly basis. Monitoring of interval times will be collated and provided to sites on a quarterly basis so that regular feedback might induce appropriately fast treatment processes. Sites that fail to meet these objectives in the trial will be dropped from the trial.

We will help, aid, abet and work with sites to achieve these targets. It is our strong conviction that in order for the intervention to work well enough to show the sought after effect size, it must be executed with military precision. This will require tremendous teamwork within the trial and within each site.

### Consent Process

In order to achieve the rapid treatment process we are seeking, one option will be to utilize the deferral of consent process for research. The emergency nature of the treatment paradigm means that obtaining a standard research consent from a surrogate (eg. spouse or family member) will result in an unacceptable time delay that would:

- (a) exclude a large proportion of patients because a surrogate consent giver is not available
- (b) nullify the potential treatment effect because of the time delay. A 30-minute time delay will result in approximately an average 10% absolute risk difference on the primary outcome. It routinely takes 30-45 minutes to obtain a proper informed consent.

This is a novel aspect of this stroke trial. Further details are provided below.

### Baseline Clinical and Laboratory Evaluations

All patients will undergo a routine neurological and clinical assessment at baseline including the NIHSS, pre-stroke Barthel Index. Routine emergency blood work will be evaluated including: CBC, PT, aPTT, serum creatinine and serum glucose. The results of this bloodwork are not required prior to randomization. If the patient is female and is of childbearing potential a pregnancy test (urine point-of-care

pregnancy test) must be completed and the result must be negative; this is the only mandatory laboratory test prior to randomization. Other laboratory or point-of-care testing may be performed at the discretion of the attending physicians and team. The study will use and collect local laboratory results and will not use a central lab. An ECG will be completed at baseline but may be completed in the first 6 hours of hospitalization; it is not required prior to randomization because it may slow down rapid treatment.

All patients will undergo rapid CT and CTA imaging. The target door-to-imaging time should be 25 minutes or less and target door-to-needle time for IV tPA treated patients should be less than 45 minutes. Routine CT and CTA imaging guidance are provided in the standard operating procedures manual.

CT quality is a critical component of the study. Each site will undergo a site visit in which the study neuroradiologist will review and discuss the CT imaging paradigm at the site. The site must agree to maximize their CT quality. This will be done on a site-by-site basis since it will be dependent upon the technical factors associated with the existing imaging infrastructure at the site.

CT angiography is mandatory for assessment of the inclusion criteria in the study. We are strongly recommending the use of a 3-phase CTA data acquisition paradigm. This will be detailed in the MOP.

CT perfusion and/or MR are not required. These imaging techniques are not prohibited by protocol; however, the stringent time requirements for initiating treatment mean that it would be very difficult to complete CTP and/or MR stroke imaging as part of the imaging work-up of these patients.

## Schedule of Assessments

|  | Baseline | 2-8 h | Day 1
(24 ±6 h from randomization) | Day 2
(48 ±6 h from randomization) | Day 5 or discharge
(±1 d) | Day 30
(±5 d) | Day 90
(±7 d)§ |
|--|----------|-------|---------------------------------------|---------------------------------------|------------------------------|------------------|-------------------|
| Informed consent or documented deferral of consent | X        |       |                                       |                                       |                              | X                | X                 |
| History and examination                            | X        |       |                                       |                                       |                              |                  |                   |
| NIHSS  | X        | X     | X                                     | X                                     | X                            | X                | X                 |
| mRS  |          |       | X¶                                    |                                       |                              | X                | X                 |
| Barthel  | X        |       |                                       |                                       |                              | X                | X                 |
| miFUNCTION   |          |       | X¶                                    |                                       |                              | X                | X                 |
| Trailmaking A, B                                   |          |       |                                       |                                       |                              |                  | X                 |
| MoCA   |          |       |                                       |                                       |                              |                  | X                 |
| Boston Naming test                                 |          |       |                                       |                                       |                              |                  | X                 |
| Sunnybrook Neglect Assessment Procedure (SNAP)     |          |       |                                       |                                       |                              |                  | X                 |
| EQ-5D  |          |       |                                       |                                       |                              | X                | X                 |
| NCCT head  | X        |       | X*                                    |                                       |                              |                  |                   |
| CTA COW  | X        | X**   |                                       |                                       |                              |                  |                   |
| Full emergency stroke labs                         | X‡       |       |                                       |                                       |                              |                  |                   |
| Creatinine and CBC only                            |          |       | X                                     |                                       |                              |                  |                   |
| ECG  | X‡       |       | X                                     |                                       |                              |                  |                   |
| Adverse event assessment                           |          | X     | X                                     | X                                     | X                            | X                | X                 |
| Prior medications                                  | X‡       |       |                                       |                                       |                              |                  |                   |
| Concomitant medications                            | X        | X     | X                                     | X                                     | X                            | X                |                   |
| Consent process survey                             |          |       | X                                     |                                       |                              |                  | X                 |

\*Day +1 NCCT head may be supplanted by an MR head at the discretion of the local site. We encourage this.

\*\*2-8 hours CTA COW – Control group only. We encourage early CTA within this time window. If there is a situation that arises where a subject randomized to the endovascular group does not have a final cerebral angiogram performed, that patient should have a 2-8h CTA to evaluate recanalization.

¶ The mRS and miFUNCTION scores at 24 hours are captured as estimates of historical (pre-stroke) scores

‡ These tests are required at baseline. Blood should be drawn at baseline, but results are not required prior to randomization. ECG should be done within 6 hours of hospital admission, but is not required prior to randomization. Prior medications should be collected but are not required prior to randomization.

§ At minimum 90d evaluations of mRS, NIHSS, BI should be performed by an evaluator blinded to the acute intervention. It is preferred if all 90d evaluation are done by a blinded evaluator.  
d = days; h = hours

## Clinical Management of the Patient

It is expected that subjects will receive the best usual standard of stroke unit care. All subjects are expected to be admitted to hospital as part of routine standard of care.

It is expected that all subjects will undergo a routine work-up for the mechanism of their stroke and be treated appropriately and definitively. This is critically important because subjects who have an excellent early recovery are at the highest risk of early recurrent stroke. We wish to prevent recurrent stroke from confounding the 30-day and 90-day clinical outcome such that patients who are well at discharge remain that way for the duration of the 90-day follow-up period.

We expect the following preventive care. Relevant patients with atrial fibrillation should be anti-coagulated. Patients with symptomatic carotid artery stenosis should undergo carotid revascularization early and definitely within 2 weeks of stroke onset. Risk factors, including hypertension, elevated cholesterol, diabetes mellitus, tobacco smoking, should be treated appropriately and aggressively according to current standards of care.

We expect patients to receive adequate hydration to prevent renal complications. Patients will receive intravenous radio-contrast media for CT angiography and in half the study population for endovascular intervention. While this medication is generally extremely safe in stroke patients, simple hydration can prevent renal complications, particularly among patients with baseline borderline renal function and among those with diabetes mellitus. Further, patients with ischemic stroke are generally slightly hypovolemic at baseline. We recommend use of intravenous normal saline (0.9% saline) infusion at 1.5 – 2.0 cc/kg/h until the subject is eating and drinking safely and well. Therefore, for the typical subject this will mean IV NS at 75-125 cc/h overnight only. We do not recommend the use of bicarbonate solutions or N-acetyl-cysteine solutions for renal protection.

For patients that are disabled from their stroke and require a longer in-patient stay and/or rehabilitation, it is expected that they will receive standard stroke unit care to prevent complications. These include:

- DVT prophylaxis for patients who are bed-bound or primarily bed-bound
- Swallowing assessments and prevention of aspiration pneumonia
- Early mobilization and physiotherapy to prevent skin breakdown, pneumonia, DVT/PE
- Early diagnosis and treatment of fever

All patients are expected to receive expert stroke unit care and then rehabilitation according to their clinical need.

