## Selection and Enrolment of Subjects

### Inclusion Criteria

#### Clinical (Heterogeneous sampling frame)

1. Acute ischemic stroke
2. Age 18 or greater
3. Onset (last-seen-well) time to randomization time < 12 hours.
4. Disabling stroke defined as a baseline NIHSS > 5 at the time of randomization.
5. Pre-stroke (24 hours prior to stroke onset) independent functional status in activities of daily living with modified Barthel Index > 90. Patient must be living in their own home, apartment or seniors lodge where no nursing care is required.

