### **Carotid artery stenting**

Some interventionalists prefer to stent a stenosed carotid artery either during or at the end of a case. We recommend that this not be done.

Tandem occlusion of the extracranial carotid at the bifurcation associated with an M1-MCA occlusion is common. The target lesion initially is the M1-MCA occlusion. Advance a catheter past the ICA lesion and deal with the M1-MCA first. Very often, in this process, the proximal ICA is open at the end of treating the M1-MCA because of the mechanical manipulation of the occlusive lesion at the carotid. What was initially a 99% stenosis is reduced to 60 or 70%.

At this point stop. Treat the subject with ASA per rectum (since they cannot swallow) and bring the subject back the following day to decide on whether to stent or pursue endarterectomy. It is simply not necessarily true that forward flow in the carotid is required to keep the M1-MCA open.

The major potential difficulty with leaving a carotid stent in place is the need for antiplatelet therapy, which will increase the chance of major symptomatic bleeding.

Very occasionally, a stent is required – either intracranially or at the carotid bifurcation. In these circumstance, we recommend using ASA and clopidogrel rather than IV abciximab or eptifibatide. Give ASA per rectum and as soon as possible give 600 mg clopidogrel per NG.

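### The flat saline rate of 75-125 cc/h does not follow from the 1.5-2.0 cc/kg/h it is said to be derived from, except for subjects of 50 to 62.5 kg

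*Protocol*

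**What the plan says.** The passage on hydration in the Protocol, Clinical Management of the Patient, applies to all subjects. It is worded as advice: "We recommend use of intravenous normal saline (0.9% saline) infusion". The rate and the stopping condition come together: "infusion at 1.5 – 2.0 cc/kg/h until the subject is eating and drinking safely and well". The next sentence turns this into a bedside figure: "Therefore, for the typical subject this will mean IV NS at 75-125 cc/h overnight only". No body weight is given there or elsewhere in the Protocol.

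The same paragraph gives the purpose, which is to prevent renal complications after contrast, particularly in subjects with borderline renal function or diabetes. Contrast nephropathy is listed under Safety Outcomes. Its definition, under Process and Quality Outcomes, is a rise in serum creatinine of 50% or more from baseline to 24 h after treatment.

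**The concern.** The flat rate is presented as a consequence of the per-kilogram rate, so the reader expects a plausible adult weight to turn one into the other. For most plausible adult weights it does not. A site that takes the flat figure as a convenient shorthand would give many subjects less than the per-kilogram recommendation. A site that calculates from weight would often exceed the flat range. Each could reasonably believe it was following the Protocol.

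What is at stake is the consistency of a supportive-care instruction whose stated aim is to protect the kidneys. A mismatch that grows with body weight would leave heavier subjects at some sites with less fluid than the per-kilogram sentence recommends.

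**Working it through.** **Inputs.** Per-kilogram rate 1.5-2.0 cc/kg/h and flat rate 75-125 cc/h, both from Clinical Management of the Patient. Body weight is not in the Protocol, so it is an assumption, shown here from 50 to 100 kg.

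**Formula.** Rate in cc/h = rate in cc/kg/h × weight in kg.

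**Step 1: try to reproduce the Protocol's figure.** Lower end: 75 / 1.5 = 50 kg. Upper end: 125 / 2.0 = 62.5 kg. The two ends need different weights. No single weight can give the flat range, because the ratio of high to low is 2.0 / 1.5 = 1.33 for the per-kilogram range and 125 / 75 = 1.67 for the flat range. This step needs no assumption about weight.

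**Step 2: apply the per-kilogram rule across weights.**

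| Weight (kg, assumed) | 1.5-2.0 cc/kg/h gives (cc/h) | Relation to 75-125 cc/h |
|---|---|---|
| 50 | 75-100 | inside |
| 60 | 90-120 | inside |
| 62.5 | 93.75-125 | inside, at the limit |
| 70 | 105-140 | 20/35 = 57% of the range inside |
| 75 | 112.5-150 | 12.5/37.5 = 33% inside |
| 80 | 120-160 | 5/40 = 12.5% inside |
| 90 | 135-180 | no overlap |
| 100 | 150-200 | no overlap |

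Overlap ends where the lowest per-kilogram rate reaches the highest flat rate: 125 / 1.5 = 83.3 kg.

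**Step 3: convert the flat rate back.** At 70 kg, 75/70 to 125/70 = 1.07-1.79 cc/kg/h. At 80 kg, 75/80 to 125/80 = 0.94-1.56 cc/kg/h. In both cases the bottom of the flat range is below the recommended 1.5 and part of the range is within the recommendation.

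**Step 4: size of the discrepancy from rate alone.** The midpoints are 1.75 cc/kg/h and 100 cc/h.
- 70 kg: 1.75 × 70 = 122.5 cc/h; 122.5 / 100 = about 1.2. Over an assumed 12 h night, 1470 against 1200 cc.
- 80 kg: 1.75 × 80 = 140 cc/h; 140 / 100 = 1.4. Over the same 12 h, 1680 against 1200 cc.

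**The case against.** The best defence of the sentence is that it gives a rounded span across subjects, not a calculation for one subject. At the lower rate alone, 75-125 cc/h covers 50 to 83.3 kg (75/1.5 to 125/1.5), and at 125 cc/h an 80 kg subject receives 1.56 cc/kg/h, which is within the recommendation. A subject above 83.3 kg might also not be the typical subject meant. All of this is fair and shows that the mismatch is moderate. It does not restore the derivation, because that reading ignores the 2.0 cc/kg/h end and the weight behind the figure is still unstated.

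Three stronger readings are tempting, and the Protocol does not support them.

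- **That the two durations contradict each other.** A reader might set the stopping condition against the overnight remark, noting that enrolment requires a "Disabling stroke defined as a baseline NIHSS > 5 at the time of randomization" and that care includes "swallowing assessment and prevention of aspiration pneumonia, NG feeding as appropriate". But the overnight remark is worded as what the stopping condition will mean for the typical subject. It is not a second rule for everyone, and a subject who cannot yet eat is covered by the first sentence. The phrase "since they cannot swallow" in Appendix 1 concerns giving aspirin after treatment of a tandem carotid lesion; it is not a statement about treated subjects in general. The remark may be optimistic for some subjects, but that is a matter of clarity.
- **That sites could differ many-fold in volume.** For an 80 kg subject, 72 h at 120-160 cc/h is 8.6-11.5 L, against 0.9-1.5 L for 12 h at 75-125 cc/h. The weight and both durations are assumed, and the comparison applies the typical-subject remark to someone it does not describe. Most of the larger volume would also run after the 24 h creatinine measurement that defines contrast nephropathy.
- **That the trial comparison is biased.** The advice is the same in both arms, allocation is 1:1, and site is one of the balancing variables listed under Study Enrolment Process. A site's reading of the sentence would therefore apply to its subjects in both arms.

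**Conclusion.** The point holds for the rate. The lack of any single weight that gives the flat range is a matter of arithmetic. Full agreement is confined to 50-62.5 kg and all overlap ends at 83.3 kg. How many subjects fall outside those limits cannot be said from the Protocol.

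The practical size, about 1.2- to 1.4-fold at range midpoints, rests on assumed weights of 70 to 80 kg. The passage is a recommendation and not a study treatment, so this is a minor correction. It bears at most on renal safety in heavier subjects and does not affect the primary analysis, the sample size or the comparison between arms. A conflict over duration is not established.

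**What to change.** In Clinical Management of the Patient, reconcile the per-kilogram and flat rates so that one expression governs. If a worked figure is kept, recompute it from that expression and state the weight or weight range assumed.

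In the same edit, settle how the overnight remark relates to the stopping condition. If it is only an illustration, as its wording suggests, say so and say that the condition in the preceding sentence governs. If something else was intended, reconcile the two. Which rate and duration stand is for the clinical leads, and no view is taken here.

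The cost is one corrected sentence and a short memo to sites. No change to data collection, sample size or analysis is needed.
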